Appendix 4. Hepatic Monitoring Tests for Treatment-Emergent Abnormality

Selected tests may be obtained in the event of a treatment-emergent hepatic abnormality and may be required in follow-up with participants in consultation with Lilly, or its designee's, clinical research physician.

Hematology	Clinical Chemistry
Hemoglobin	Total bilirubin
Hematocrit	Direct bilirubin
Erythrocytes (RBCs - red blood cells)	Alkaline phosphatase (ALP)
Leukocytes (WBCs - white blood cells)	Alanine aminotransferase (ALT)
Differential:	Aspartate aminotransferase (AST)
Neutrophils, segmented	Gamma-glutamyl transferase (GGT)
Lymphocytes	Creatine kinase (CK)
Monocytes	Other Chemistry
Basophils	Acetaminophen
Eosinophils	Acetaminophen protein adducts
Platelets	Alkaline phosphatase isoenzymes
Cell morphology (RBC and WBC)	Ceruloplasmin
	Copper
Coagulation	Ethyl alcohol (EtOH)
Prothrombin time, INR (PT-INR)	Haptoglobin
Serology	Immunoglobulin A (IgA, quantitative)
Hepatitis A virus (HAV) testing:	Immunoglobulin G (IgG, quantitative)
HAV total antibody	Immunoglobulin M (IgM, quantitative)
HAV IgM antibody	Phosphatidylethanol (PEth)
Hepatitis B virus (HBV) testing:	Urine Chemistry
Hepatitis B surface antigen (HBsAg)	Drug screen
Hepatitis B surface antibody (anti-HBs)	Ethyl glucuronide (EtG)
Hepatitis B core total antibody (anti-HBc)	Other Serology
Hepatitis B core IgM antibody	Anti-nuclear antibody (ANA)
Hepatitis B core IgG antibody	Anti-smooth muscle antibody (ASMA) ^a
HBV DNA ^c	Anti-actin antibody ^b

Hematology	Clinical Chemistry
Hepatitis C virus (HCV) testing:	Epstein-Barr virus (EBV) testing:
HCV antibody	EBV antibody
HCV RNA ^c	EBV DNA ^c
Hepatitis D virus (HDV) testing:	Cytomegalovirus (CMV) testing:
HDV antibody	CMV antibody
Hepatitis E virus (HEV) testing:	CMV DNA ^c
HEV IgG antibody	Herpes simplex virus (HSV) testing:
HEV IgM antibody	HSV (Types 1 and 2) antibody
HEV RNA ^c	HSV (Types 1 and 2) DNA ^c
Microbiology^d	Liver kidney microsomal type 1 (LKM-1) antibody
Culture:	
Blood	
Urine	

Abbreviation: INR = international normalized ratio.

^aNot required if anti-actin antibody is tested.

^bNot required if anti-smooth muscle antibody (ASMA) is tested.

^cReflex/confirmation dependent on regulatory requirements, testing availability, or both.

^dAssayed ONLY by investigator-designated local laboratory; no central testing available.

The Lilly-designated central laboratory must complete the analysis of all selected testing except for microbiology testing.

Local testing may be performed in addition to central testing when necessary for immediate participant management.

Results will be reported if a validated test or calculation is available.

Appendix 5. Adverse Events: Definitions and Procedures for Recording, Evaluating, Follow-Up, and Reporting

- The definitions and procedures detailed in this appendix are in accordance with International Organization for Standardization (ISO) 14155.
- Both the investigator and the sponsor will comply with all local medical device reporting requirements.
- The detection and documentation procedures described in this protocol apply to all sponsor medical devices provided for use in the study. See Section 9.2 for the list of sponsor medical devices.

Definition of AE

AE Definition

• An AE is any untoward medical occurrence in a participant administered a pharmaceutical product and that does not necessarily have a causal relationship with the study intervention. An AE can therefore be any unfavorable and unintended sign (including an abnormal laboratory finding), symptom, or disease (new or exacerbated) temporally associated with the use of a medicinal (investigational) product, whether or not related to the medicinal (investigational) product.• An AE is any untoward medical occurrence, unintended disease or injury, or untoward clinical signs (including abnormal laboratory finding) in study participants, users, or other persons, whether or not related to the investigational medical device. This definition includes events related to the investigational medical device or comparator and events related to the procedures involved except for events in users or other persons, which only include events related to investigational devices.

Events Meeting the AE Definition

- Any abnormal laboratory test results (hematology, clinical chemistry, or urinalysis) or other safety assessments (for example, ECG, radiological scans, vital signs measurements), including those that worsen from baseline, considered clinically significant in the medical and scientific judgment of the investigator (that is, not related to progression of underlying disease).
- Exacerbation of a chronic or intermittent pre-existing condition including either an increase in frequency and/or intensity of the condition.
- New condition detected or diagnosed after study intervention administration even though it may have been present before the start of the study.
- Signs, symptoms, or the clinical sequelae of a suspected drug–drug interaction.
- Medication error, misuse, or abuse of IMP, including signs, symptoms, or clinical sequelae.
- Signs, symptoms, or the clinical sequelae of a suspected overdose of either study intervention or a concomitant medication. Overdose per se will not be reported as an AE or SAE unless it

is an intentional overdose taken with possible suicidal or self-harming intent. Such overdoses should be reported regardless of sequelae.

- Lack of efficacy or failure of expected pharmacological action per se will not be reported as an AE or SAE. Such instances will be captured in the efficacy assessments. However, the signs, symptoms, and/or clinical sequelae resulting from lack of efficacy will be reported as AE or SAE if they fulfil the definition of an AE or SAE.

Events NOT Meeting the AE Definition

- Any clinically significant abnormal laboratory findings or other abnormal safety assessments that are associated with the underlying disease, unless judged by the investigator to be more severe than expected for the participant's condition.
- The disease/disorder being studied or expected progression, signs, or symptoms of the disease/disorder being studied, unless more severe than expected for the participant's condition.
- Medical or surgical procedure (for example, endoscopy, appendectomy). Note: The condition that leads to the procedure is the AE.
- Situations in which an untoward medical occurrence did not occur (social and/or convenience admission to a hospital). Anticipated day-to-day fluctuations of pre-existing diseases or conditions present or detected at the start of the study that do not worsen.

Definition of SAE

An SAE is defined as any untoward medical occurrence that, at any dose, meets one or more of the criteria listed:

- a. Results in death**

b. Is life-threatening

The term “life-threatening” in the definition of “serious” refers to an event in which the participant was at risk of death at the time of the event. It does not refer to an event that hypothetically might have caused death, if the event were more severe.

c. Requires in-participant hospitalization or prolongation of existing hospitalization

- In general, hospitalization signifies that the participant has been admitted to the hospital for observation and/or treatment that would not have been appropriate in the physician’s office or out-participant setting. Complications that occur during hospitalization are AEs. If a complication prolongs hospitalization or fulfills any other serious criteria, the event is serious. When in doubt as to whether “hospitalization” occurred or was necessary, the AE should be considered serious.
- Hospitalization for elective treatment of a pre-existing condition that did not worsen from baseline is not considered an AE.

d. Results in persistent disability/incapacity

- The term “disability” means a substantial disruption of a person’s ability to conduct normal life functions.
- This definition is not intended to include experiences of relatively minor medical significance such as uncomplicated headache, nausea, vomiting, diarrhea, influenza, and accidental trauma (for example, sprained ankle) that may interfere with or prevent everyday life functions but do not constitute a substantial disruption.

e. Is a congenital anomaly/birth defect

- Abnormal pregnancy outcomes (for example, spontaneous abortion, fetal death, stillbirth, congenital anomalies, ectopic pregnancy) are considered SAEs.

f. Other situations:

- Medical or scientific judgment should be exercised in deciding whether SAE reporting is appropriate in other situations such as important medical events that may not be immediately life-threatening or result in death or hospitalization but may jeopardize the participant or may require medical or surgical intervention to prevent one of the other outcomes listed in the above definition. These events should usually be considered serious.
- Examples of such events include invasive or malignant cancers, intensive treatment in an emergency room or at home for allergic bronchospasm, blood dyscrasias or convulsions that do not result in hospitalization, or development of drug dependency or drug abuse.

g. Resulted in medical or surgical intervention to prevent life-threatening illness or injury or permanent impairment to a body structure or a body function**Definition of Product Complaints****Product Complaint**

- A PC is any written, electronic, or oral communication that alleges deficiencies related to the identity, quality, durability, reliability, safety, effectiveness, or performance of a study intervention. When the ability to use the study intervention safely is impacted, the following are also PCs:
 - Deficiencies in labeling information, and
 - Use errors for device or drug-device combination products due to ergonomic design elements of the product.
- PCs related to study interventions used in clinical trials are collected in order to ensure the safety of participants, monitor quality, and to facilitate process and product improvements.
- Investigators will instruct participants to contact the site as soon as possible if he or she has a PC or problem with the study intervention so that the situation can be assessed.
- An event may meet the definition of both a PC and an AE/SAE. In such cases, it should be reported as both a PC and as an AE/SAE.

Recording and Follow-up of AE and/or SAE and Product Complaints

AE, SAE, and PC Recording

When an AE/SAE occurs, it is the responsibility of the investigator to review all documentation (for example, hospital progress notes, laboratory reports, and diagnostics reports) related to the event.The investigator will then record all relevant AE/SAE information in the participant's medical records, in accordance with the investigator's normal clinical practice. AE/SAE information is reported on the appropriate CRF page and PC information is reported on the Product Complaint Form. 
Note: An event may meet the definition of both a PC and an AE/SAE. In such cases, it should be reported as both a PC and as an AE/SAE.
 
It is not acceptable for the investigator to send photocopies of the participant's medical records to the sponsor or designee in lieu of completion of the AE/SAE CRF page for AE/SAE and the PC Form for PCs.There may be instances when copies of medical records for certain cases are requested by the sponsor or designee. In this case, all participant identifiers, with the exception of the participant number, will be redacted on the copies of the medical records before submission to the sponsor or designee.The investigator will attempt to establish a diagnosis of the event based on signs, symptoms, and other clinical information. Whenever possible, the diagnosis (not the individual signs/symptoms) will be documented as the AE/SAE.

Assessment of Intensity

The investigator will make an assessment of intensity for each AE and SAE reported during the study and assign it to 1 of the following categories:
 
Mild: An event that is easily tolerated by the participant, causing minimal discomfort and not interfering with everyday activities.Moderate: An event that causes sufficient discomfort and interferes with normal everyday activities.Severe: An event that prevents normal everyday activities. An AE that is assessed as severe should not be confused with an SAE. Severe is a category utilized for rating the intensity of an event; and both AEs and SAEs can be assessed as severe. 
An event is defined as "serious" when it meets at least 1 of the predefined outcomes as described in the definition of an SAE, not when it is rated as severe.

Assessment of Causality

• The investigator is obligated to assess the relationship between study intervention and each occurrence of each AE/SAE.• A “reasonable possibility” of a relationship conveys that there are facts, evidence, and/or arguments to suggest a causal relationship, rather than a relationship cannot be ruled out.• The investigator will use clinical judgment to determine the relationship.• Alternative causes, such as underlying disease(s), concomitant therapy, and other risk factors, as well as the temporal relationship of the event to study intervention administration will be considered and investigated.• The investigator will also consult the Investigator’s Brochure (IB) in his/her assessment.• For each AE/SAE, the investigator must document in the medical notes that he/she has reviewed the AE/SAE and has provided an assessment of causality.• There may be situations in which an SAE has occurred and the investigator has minimal information to include in the initial report to Sponsor or designee. However, it is very important that the investigator always make an assessment of causality for every event before the initial transmission of the SAE data to Sponsor or designee.• The investigator may change his/her opinion of causality in light of follow-up information and send an SAE follow-up report with the updated causality assessment.• The causality assessment is one of the criteria used when determining regulatory reporting requirements.

Follow-Up of AEs and SAEs

• The investigator is obligated to perform or arrange for the conduct of supplemental measurements and/or evaluations as medically indicated or as requested to elucidate the nature and/or causality of the AE or SAE as fully as possible. This may include additional laboratory tests or investigations, histopathological examinations, or consultation with other health care professionals.• If a participant dies during participation in the study or during a recognized follow-up period, the investigator will provide a copy of any post-mortem findings including histopathology.

Reporting of SAEs

SAE Reporting via an Electronic Data Collection Tool

• The primary mechanism for reporting an SAE to the sponsor or the sponsor’s designee will be the electronic data collection tool.• If the electronic system is unavailable or if a pregnancy is reported, then the site will use the paper SAE or pregnancy data collection tools to report the event within 24 hours.• The site will enter SAE data into the electronic system as soon as it becomes available.

- After the study is completed at a given site, the electronic data collection tool will be taken offline to prevent the entry of new data or changes to existing data.
- If a site receives a report of a new SAE from a study participant or receives updated data on a previously reported SAE after the electronic data collection tool has been taken offline, then the site can report this information on a paper SAE form or to the medical monitor or SAE by telephone.
- Contacts for SAE reporting can be found in the site training documents.

Reporting of SAEs

SAE Reporting via Paper Form

- Facsimile transmission of the SAE paper CRF is the preferred method to transmit this information to the medical monitor or the SAE coordinator.
- Initial notification via telephone does not replace the need for the investigator to complete and sign the SAE CRF pages within the designated reporting time frames.
- Contacts for SAE reporting can be found in the site training documents.

Regulatory Reporting Requirements

SAE Regulatory Reporting

- Prompt notification by the investigator to the sponsor of a SAE is essential so that legal obligations and ethical responsibilities toward the safety of participants and the safety of a study intervention under clinical investigation are met.
- The sponsor has a legal responsibility to notify both the local regulatory authority and other regulatory agencies about the safety of a study intervention under clinical investigation. The sponsor will evaluate the reported SAEs, including confirmation of relatedness and assessment of expectedness. The sponsor has processes for safety reports for identification, recording, and expedited reporting of SUSARs according to local regulatory requirements. The sponsor will comply with country-specific regulatory requirements relating to safety reporting to the regulatory authority, IRB/IEC, and investigators.
- An investigator who receives an investigator safety report describing a SAE or other specific safety information (for example, summary or listing of SAEs) from the sponsor will review and then file it along with the IB will notify the IRB/IEC, if appropriate according to local requirements.

Appendix 6. Contraceptive Guidance and Collection of Pregnancy Information

Definitions

Woman of Childbearing Potential (WOCBP)

A woman is considered fertile following menarche and until becoming post-menopausal unless permanently sterile (see below).

If fertility is unclear (e.g., amenorrhea in adolescents or athletes) and a menstrual cycle cannot be confirmed before first dose of study intervention, additional evaluation should be considered.

Women in the following categories are not considered WOCBP

1. Premenarchal
2. Premenopausal female with 1 of the following:
 - Documented hysterectomy
 - Documented bilateral salpingectomy
 - Documented bilateral oophorectomy

For individuals with permanent infertility due to an alternate medical cause other than the above, (e.g., mullerian agenesis, androgen insensitivity), investigator discretion should be applied to determining study entry.

Note: Documentation can come from the site personnel's: review of the participant's medical records, medical examination, or medical history interview.

3. Postmenopausal female is defined as, women with:
 - At least 6 weeks post-surgical bilateral oophorectomy with or without hysterectomy, confirmed by operative note.
OR
 - With spontaneous amenorrhea for at least 12 months, not induced by a medical condition such as anorexia nervosa and not taking medications during the amenorrhea (e.g. oral contraceptives, hormones, gonadotropin releasing hormone, anti-estrogens, selective estrogen receptor modulators (SERMs), or chemotherapy that induced the amenorrhea. And if \leq age 50, has an FSH of ≥ 40 mIU/mL and estradiol of ≤ 30 pg/mL.

Contraception guidance for women of childbearing potential (WOCBP):

This outlines the rules for WOCBP to ensure they do not become pregnant during the study.

See guidance for specific patient populations below:

Women of childbearing potential who are completely abstinent as their preferred and

usual lifestyle or in a same-sex relationship as their preferred and usual lifestyle:

Must...	Must not...
agree to either remain abstinent or stay in a same-sex relationship without sexual relationships with males	
 use periodic abstinence methods 
 calendar ovulation sympto-thermal, or postovulation declare abstinence just for the duration of a trial, or use the withdrawal method

Women of childbearing potential who are NOT completely abstinent as their preferred and usual lifestyle, or NOT in a same-sex relationship as their preferred and usual lifestyle, must do the following:

Topic	Condition
Pregnancy testing	Have a negative (serum/urine) test result at screening followed by a negative (urine/serum) result within 24 hours prior to treatment exposure. See the protocol Schedule of Activities for subsequent pregnancy testing requirements.
Contraception	
Agree to use 1 highly effective method of contraception, or a combination of 2 effective methods of contraception.
 
These forms of contraception must be used for the duration of the study.

Examples of different forms of contraception:

Methods	Examples
Highly effective contraception (less than 1% failure rate)	
 female sterilization combination oral contraceptive pill progestin-only contraceptive pill (mini-pill) implanted contraceptives injectable contraceptives contraceptive patch (only women <198 pounds or 90 kg) total abstinence vasectomy (if only sexual partner) fallopian tube implants (if confirmed by hysterosalpingogram) combined contraceptive vaginal ring, or intrauterine devices

Effective contraception	
• male or female condoms with spermicide• diaphragms with spermicide or cervical sponges• barrier method with use of a spermicide
◦ condom with spermicide◦ diaphragm with spermicide, or◦ female condom with spermicide 
Note: The barrier method must include use of a spermicide (that is, condom with spermicide, diaphragm with spermicide, or female condom with spermicide) to be considered effective.

Ineffective forms of contraception whether used alone or in any combination	
• spermicide alone• periodic abstinence• fertility awareness (calendar method, temperature method, cervical mucus, or symptothermal)• withdrawal• postcoital douche, or• lactational amenorrhea

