5.1.5. Post-Treatment Follow-Up Period

Participants who have received at least 1 dose of study drug (including those who do not enter in the LTE period or discontinued early) should enter the PTFU period for a minimum of 12 weeks after their last regularly scheduled visits (or the date of their ETV). Required study visits should occur at 4 weeks after and at 8 weeks after the last regularly scheduled visit (or the date of the participant's ETV) (Visits 801 and 802, respectively), except for participants with concurrent infections that require systemic anti-infective therapy (described below).

If, at the last scheduled visit or ETV, a participant's neutrophil count is <1500 cells/ μ L ($<1.50 \times 10^3/\mu\text{L}$ or <1.50 GI/L) and less than the participant's baseline neutrophil count, the following measures should be taken:

- Participants with concurrent infection: If there is a concurrent infection that requires systemic anti-infective therapy, the participant should receive appropriate medical care and a repeat test for neutrophil count should be performed at least Q4W (or sooner as appropriate) until resolution of infection. Upon resolution of infection, the neutrophil count should be monitored using the required study visits in the PTFU period design at Visits 801 (4 weeks after resolution of infection), 802 (8 weeks after last visit), and 803 (if necessary; 12 weeks after last visit); additional visits may be required depending on the degree of neutropenia.
- Participants without concurrent infection: If there is no concurrent infection that requires systemic anti-infective therapy, the neutrophil count should be monitored using the required study visits in the PTFU period design, Visits 801 (4 weeks post ETV or last regularly scheduled visit), 802, and 803 (if necessary); additional visits may be required depending on the degree of neutropenia.
- For Visit 801 and subsequent visits, the following monitoring applies:
 - As long as a participant's neutrophil count is <1000 cells/ μ L ($<1.00 \times 10^3/\mu\text{L}$ or <1.00 GI/L) at any follow-up visit, the participant should return for additional visits at least Q4W (unscheduled visits may be required).

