6.1. Inclusion Criteria

Participants are eligible to be included in the study only if they meet all of the following criteria at enrollment:

Type of Participant and Disease Characteristics

- [1] Have a diagnosis with onset before the age of 16 years of any of the following categories of JIA as defined by the ILAR criteria (Petty et al. 2004):
 - ERA
 - JPsA
- [2] Have at least 3 active peripheral joints at screening and baseline. Active peripheral joint is defined as the presence of joint swelling or, in the absence of swelling, joint with limitation of motion plus pain on motion and/or tenderness on palpation.

Participant Characteristics

- [3] Participants with ERA must be from 6 to less than 18 years of age at screening and baseline.

Participants with JPsA must be from 2 to less than 18 years of age at screening and baseline.

Full date of birth will be collected except in countries in which it is not allowed.

- [4] Participants must weigh at least 10.0 kg.
- [5] Male or nonpregnant, non-breastfeeding female participants.

Participants of childbearing potential who are abstinent (if this is complete abstinence, as their preferred and usual lifestyle).

Total abstinence is defined as refraining from intercourse during the entirety of the study and for at least 12 weeks following the last dose of investigational product. Periodic abstinence such as calendar, ovulation, symptothermal, post ovulation methods, and withdrawal are not acceptable methods of contraception.

Otherwise, participants and their partners of childbearing potential must agree to use 2 effective methods of contraception, where at least 1 form is highly effective for the entirety of the study and for at least 12 weeks following the last dose of ixekizumab. Participants and their partners of childbearing potential must agree to use contraception for 5 months after the last dose of adalimumab.

The following contraception methods are considered acceptable (the participant, and their partner, should choose 2, and 1 must be highly effective [defined as less than 1% failure rate per year when used consistently and correctly]):

- Highly effective birth control methods:
 - Combined (estrogen- and progestogen containing) hormonal contraception associated with inhibition of ovulation: oral, intravaginal, or transdermal
 - Progestogen-only hormonal contraception associated with inhibition of ovulation: oral, intravaginal, or implantable

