 - Intrauterine device/intrauterine hormone releasing system
 - Vasectomized partner (with appropriate post vasectomy documentation of the absence of sperm in the ejaculate).
- Effective birth control methods:
 - Male or female condom with spermicide. It should be noted that the use of male and female condoms as a double barrier method is not considered acceptable due to the high failure rate when these methods are combined.
 - Diaphragm with spermicide
 - Cervical sponge
 - Cervical cap with spermicide

Note: When local guidelines concerning highly effective or effective methods of birth control differ from the above, the local guidelines must be followed.

Adolescent females who have started menses (even 1 cycle and any amount of spotting) are considered to be of childbearing potential.

Women of nonchildbearing potential are not required to use birth control and they are defined as:

- Women who are infertile due to surgical sterilization (hysterectomy, bilateral oophorectomy, or tubal ligation) and congenital anomaly such as Müllerian agenesis.

[6] All immunizations (live vaccines) are up-to-date in agreement with current immunization guidelines as noted by country specific pediatric authorities.

Informed Consent

[7] Both the child or adolescent and a parent or legal guardian are able to understand and fully participate in the activities of the clinical study and sign their assent and consent, respectively, in accordance to local guidelines.

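### Appendix 6 sets a looser contraception rule than inclusion criterion 5, both in the methods it accepts and in leaving out any period after the last dose

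*Protocol*

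**What the plan says.** **Section 6.1, criterion 5.** Participants and partners of childbearing potential who are not abstinent "must agree to use 2 effective methods of contraception, where at least 1 form is highly effective for the entirety of the study". The text introducing the list of acceptable methods repeats the rule: they "should choose 2, and 1 must be highly effective". The obligation continues "for at least 12 weeks following the last dose of ixekizumab", and a separate sentence says that they "must agree to use contraception for 5 months after the last dose of adalimumab". A note under the list adds: "When local guidelines concerning highly effective or effective methods of birth control differ from the above, the local guidelines must be followed".

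**Appendix 6.** Women of childbearing potential in the same situation must "Agree to use 1 highly effective method of contraception, or a combination of 2 effective methods of contraception". On duration it says: "These forms of contraception must be used for the duration of the study". It gives no period after the last dose of either drug.

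**Length of the study.** Section 5.1 counts the post-treatment follow-up period as part of total study duration. Section 5.1.5 gives that period a minimum of 12 weeks, but then says: "Required study visits should occur at 4 weeks after and at 8 weeks after the last regularly scheduled visit" (or after the early termination visit). The 12-week visit (Visit 803) is held only if needed.

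**Status of the criteria.** Section 6.1 makes eligibility depend on meeting every listed criterion at enrolment, and Section 6 does not permit waivers of enrolment criteria.

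**The concern.** Two parts of one protocol give the same group of participants different instructions, and the appendix is the less demanding. A site that works from Appendix 6 may accept contraception that a binding entry criterion does not accept. It may also tell a participant leaving on adalimumab that her obligation ends with her last study visit. Each such enrolment would be a deviation that the protocol does not allow to be approved in advance.

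The matter outlasts enrolment. Treatment can run to Week 264, and Section 6.1 treats any adolescent who has started menses as being of childbearing potential. A girl who is premenarchal at entry can therefore come under the contraception rules later, when nobody is re-reading the entry criteria. In the long-term extension, the pregnancy-test rows of Tables RHCG.2.3 and RHCG.2.6, and Section 9.4.5, refer sites to Appendix 6 for pregnancy testing, so that is the page they are likely to have open. The protocol's own benefit/risk section says that human data are too few to establish the safety of ixekizumab in pregnancy.

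**Working it through.** No sample-size or power figure is involved. The check compares the two sections and then works out a timeline.

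**Step 1: methods.** Take each pattern of use by a non-abstinent woman of childbearing potential, judged on the number and class of methods:

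| Pattern | Appendix 6 | Criterion 5 |
|---|---|---|
| One highly effective method alone (e.g. an intrauterine device) | meets | fails |
| Two effective methods, neither highly effective (e.g. male condom with spermicide plus diaphragm with spermicide) | meets | fails |
| One highly effective plus one effective method | meets | meets |

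On number and class, nothing that satisfies criterion 5 fails Appendix 6. The mismatch runs one way.

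**Step 2: duration, adalimumab.** Criterion 5 asks for 5 months: 5 × 365.25 / 12 / 7 = 21.7 weeks. Take a participant who stays on adalimumab to Week 104 and does not switch. With dosing every 2 weeks, assume the last dose falls at Week 102 or Week 104. Visit 802 is at Week 104 + 8 = 112. A 12-week follow-up ends at Week 104 + 12 = 116. Shortfall = 21.7 − (end of follow-up − last dose):

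| Last dose | Follow-up ends Week 112 | Follow-up ends Week 116 |
|---|---|---|
| Week 102 | 21.7 − 10 = 11.7 weeks | 21.7 − 14 = 7.7 weeks |
| Week 104 | 21.7 − 8 = 13.7 weeks | 21.7 − 12 = 9.7 weeks |

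The shortfall is about 8 to 14 weeks. A participant who switches to ixekizumab and stays in the study for more than 5 months has none, because the Appendix 6 obligation covers her throughout.

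**Step 3: duration, ixekizumab.** Criterion 5 asks for at least 12 weeks.

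- Extension completer: the Schedule of Activities shows the last administration at Visit 68 (Week 260) and none at Visit 69 (Week 264). Visit 802 is at 264 + 8 = 272, and 272 − 260 = 12 weeks. Shortfall: zero.
- Last dose at or near the last visit or early termination visit, with follow-up ending at Visit 802: 12 − 8 = 4 weeks.
- The same case with follow-up running 12 weeks: 12 − 12 = zero.

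The range is zero to about 4 weeks. SAP Section 6.1.2.3 places an injection at Week 264. If that were so, a completer would fall under the second or third case, still within the range. These figures ignore the ±7-day visit windows.

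**Step 4: does any text settle it?** The note on local guidelines covers differences from local guidance and does not rank criterion 5 against Appendix 6. Section 6.1 settles who is eligible. Nothing settles which rule a site follows for a participant already enrolled.

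**The case against.** The best reply is that eligibility is not in doubt. Section 6.1 sets it, and Appendix 2 points to Section 6 for inclusion and exclusion requirements. Appendix 6 is headed as guidance. A site that applies criterion 5 never breaches Appendix 6 on the number and class of methods, so a careful site has a safe course. That stands, and it is why the point is framed as running one way. A reader might infer that the two texts leave eligibility itself undetermined; the documents do not support that.

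The reply can add that few participants are affected. The adalimumab arm is planned at about 20, and only its non-abstinent females of childbearing potential who stop the drug and leave within 5 months meet the gap. The documents give no count for that subgroup. Other safeguards exist: urine pregnancy tests at each follow-up visit, discontinuation of treatment on pregnancy, and pregnancy reporting after the last dose. These limit the consequence, but they detect a pregnancy and do not say what contraception is required or for how long.

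The reply fails on the appendix being mere guidance. Its text presents itself as rules for women of childbearing potential and uses mandatory wording, so a site could reasonably treat it as sufficient.

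**Conclusion.** The inconsistency is real and should be corrected. Two patterns of use meet Appendix 6 and fail criterion 5. The missing post-dose period leaves a shortfall of about 8 to 14 weeks against the 5-month adalimumab requirement for participants who stop adalimumab and leave the study. For ixekizumab it is zero to about 4 weeks, depending on when the last dose falls and whether follow-up runs 12 weeks or ends at Visit 802.

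A reader might infer that Appendix 6 drops the whole 12 weeks, or the whole 5 months. That would require the study to end at the last dose, and Section 5.1 counts post-treatment follow-up as part of the study.

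The size rests on three assumptions: the study lasts to the end of the participant's own follow-up, the last adalimumab dose falls 0 to 2 weeks before the last regular visit, and visits occur on their nominal dates. The scope is non-abstinent women of childbearing potential, since the Appendix 6 rule does not extend to male participants or partners as criterion 5 does. This is a conflict of wording about eligibility and safety conduct. It does not touch the endpoint, the sample size or the Bayesian primary analysis.

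**What to change.** Reconcile criterion 5 and Appendix 6 to a single statement of the methods required and of the post-dose duration for each drug, placed in one section and cross-referenced from the other. Which rule is adopted is for the sponsor and its clinical and regulatory advisers; this review does not propose one.

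The same edit should cover three related points:

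- State whether the duration of the study runs to Visit 802 or to 12 weeks of follow-up, since Section 5.1.5 supports both.
- State whether the rule covers partners and male participants as well as women of childbearing potential.
- Align the lists of methods. Appendix 6 counts injectable contraceptives as highly effective, whereas criterion 5's list does not name them.

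The cost is protocol wording and notice to sites. No analysis, sample size or visit needs to change on account of this point.
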